9.2 Clinical Laboratory Tests

Summary statistics for mean and mean change from baseline in the routine clinical laboratory measurements, prolactin concentrations, coagulation parameters (PT, aPTT, and INR), HbA1c, and TSH will be provided by treatment and by visit.

Potentially clinically relevant laboratory measurement test results in the double-blind treatment period will be identified for the Safety Sample and will be summarized by treatment group and listed. Criteria for identifying laboratory values of potential clinical relevance are provided in [Appendix 2](#).

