16.	
Subjects who currently have clinically significant neurological, hepatic, renal, metabolic, hematological, immunological, cardiovascular, pulmonary, or gastrointestinal disorders such as the following:
 
 • any history of myocardial infarction or congestive heart failure (whether controlled or uncontrolled), • HIV seropositive status or acquired immunodeficiency syndrome, chronic hepatitis B or C (defined as positive serology and AST or ALT elevated to $> 2 \times$ ULN). 
Medical conditions that are minor or well-controlled may be considered acceptable if the condition does not expose the subject to an undue risk of a significant AE or interfere with assessments of safety or efficacy during the course of the trial. The medical monitor should be contacted in any instance where the investigator is uncertain regarding the stability of a subject's medical condition(s) and the potential impact of the condition(s) on trial participation. Subjects who are severely obese, as confirmed by a correspondingly high BMI, need to be reviewed and discussed with the medical monitor.

17.	
Subjects with IDDM (ie, any subjects using insulin) are excluded. Subjects with non-IDDM may be eligible for the trial if their condition is stable as determined by satisfying ALL of the following criteria:
 
 • HbA_{1c} $< 7.0\%$, AND • Screening glucose must be ≤ 125 mg/dL (fasting) or < 200 mg/dL (nonfasting). If the nonfasting screening glucose is ≥ 200 mg/dL, subjects must be retested in a fasted state and the retest value must be ≤ 125 mg/dL, AND • Subject has been maintained on a stable regimen of oral anti-diabetic medication(s) for at least 28 days prior to screening or diabetes has been well-controlled by diet for at least 28 days prior to screening, AND • Subject has not had any hospitalizations within the 12 months prior to screening due to diabetes or complications related to diabetes, AND • Subject's diabetes is not newly diagnosed during screening for the trial.

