18.	
Subjects with uncontrolled hypertension (DBP > 95 mmHg in any position) or symptomatic hypotension, or orthostatic hypotension which is defined as a decrease of ≥ 30 mmHg in SBP and/or a decrease of ≥ 20 mmHg in DBP after at least 3 minutes standing compared to the previous supine blood pressure, OR development of symptoms.
 
NOTE: Blood pressure measurements may be repeated once to ensure reproducibility of the exclusionary result(s) before excluding a subject based on the criteria noted above.

19.	Subjects with epilepsy or a history of seizures, except for a single seizure episode; for instance childhood febrile, post traumatic, or alcohol withdrawal seizure.
20.	Subjects with a history of a gastric bypass surgery that creates a malabsorptive state, including Roux-en-Y gastric bypass and biliopancreatic bypass with duodenal switch. This does not include gastric banding, gastric stapling, and sleeve gastrectomy procedures.

Table 3.4.3-1 Exclusion Criteria	
	Physical and Laboratory Results
21.	
Subjects with abnormal laboratory tests results, vital signs results, or ECG findings, unless, based on the investigator's judgment, the findings are not medically significant and would not impact the safety of the subject or the interpretation of the trial results. The medical monitor should be contacted to discuss individual cases, as needed. Criteria are provided in Section 3.7.3.2. In addition, subjects with the following laboratory test and ECG results at screening must be excluded from the trial:
 
 • Platelets $\leq 75000/\text{mm}^3$ • Hemoglobin $\leq 9 \text{ g/dL}$ • Neutrophils, absolute $\leq 1000/\text{mm}^3$ • AST $> 2 \times \text{ULN}$ • ALT $> 2 \times \text{ULN}$ • CPK $> 3 \times \text{ULN}$, unless discussed with and approved by the medical monitor • Creatinine $\geq 2 \text{ mg/dL}$ • QTcF $\geq 450 \text{ msec}$ in men and $\geq 470 \text{ msec}$ in women, unless due to ventricular pacing. 
Tests with exclusionary results should be repeated to ensure reproducibility of the abnormality before excluding a subject based on the criteria noted above. For ECG, perform 3 consecutive recordings. If 2 of the 3 remain exclusionary then the subject must be excluded.

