Appendix 1 Criteria for Identifying Vital Signs of Potential Clinical Relevance

Variable	Criterion Value ^a	Change Relative to Baseline ^a
Heart Rate ^b	> 120 bpm < 50 bpm	≥ 15 bpm increase ≥ 15 bpm decrease
Systolic Blood Pressure ^b	> 180 mmHg < 90 mmHg	≥ 20 mmHg increase ≥ 20 mmHg decrease
Diastolic Blood Pressure ^b	> 105 mmHg < 50 mmHg	≥ 15 mmHg increase ≥ 15 mmHg decrease
Orthostatic Hypotension	≥ 20 mmHg decrease in systolic blood pressure and a ≥ 25 bpm increase in heart rate from supine to sitting/standing	Not Applicable (baseline status not considered)
Weight	-	≥ 7% increase ≥ 7% decrease

^a In order to be identified as potentially clinically relevant, an on-treatment value must meet the “Criterion Value” and also represent a change from the subject’s baseline value of at least the magnitude shown in the “Change Relative to Baseline” column.

^b As defined in “Supplementary Suggestions for Preparing an Integrated Summary of Safety Information in an Original NDA Submission and for Organizing Information in Periodic Safety Updates,” FDA Division of Neuropharmacological Drug Products draft (2/27/87).

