Appendix 2 Criteria for Identifying Laboratory Values of Potential Clinical Relevance

Laboratory Tests		Criteria
Chemistry		
AST (SGOT)		$\geq 3 \times$ upper limit of normal (ULN)
ALT (SGPT)		$\geq 3 \times$ ULN
Alkaline phosphatase		$\geq 3 \times$ ULN
Lactate dehydrogenase (LDH)		$\geq 3 \times$ ULN
Blood urea nitrogen (BUN)		≥ 30 mg/dL
Creatinine		≥ 2.0 mg/dL
Uric Acid		
Men		≥ 10.5 mg/dL
Women		≥ 8.5 mg/dL
Bilirubin (total)		≥ 2.0 mg/dL
Creatine phosphokinase (CPK)		$\geq 3 \times$ ULN
Prolactin		$>$ ULN
Hematology		
Hematocrit		
Men		$\leq 37\%$ and decrease of ≥ 3 percentage points from Baseline
Women		$\leq 32\%$ and decrease of ≥ 3 percentage points from Baseline
Hemoglobin		
Men		≤ 11.5 g/dL
Women		≤ 9.5 g/dL
White blood count		$\leq 2,800/\text{mm}^3$ or $\geq 16,000/\text{mm}^3$
Eosinophils		$\geq 10\%$
Neutrophils		$\leq 15\%$
Absolute neutrophil count		$\leq 1,000/\text{mm}^3$
Platelet count		$\leq 75,000/\text{mm}^3$ or $\geq 700,000/\text{mm}^3$
Urinalysis		
Protein		Increase of ≥ 2 units
Glucose		Increase of ≥ 2 units
Casts		Increase of ≥ 2 units
Additional Criteria		
Chloride		≤ 90 mEq/L or ≥ 118 mEq/L
Potassium		≤ 2.5 mEq/L or ≥ 6.5 mEq/L
Sodium		≤ 126 mEq/L or ≥ 156 mEq/L
Calcium		≤ 8.2 mg/dL or ≥ 12 mg/dL
Glucose		
Fasting		≥ 100 mg/dL
Non-Fasting		≥ 200 mg/dL
Total Cholesterol, Fasting		≥ 240 mg/dL
LDL Cholesterol, Fasting		≥ 160 mg/dL
HDL Cholesterol, Fasting		
Men		< 40 mg/dL
Women		< 50 mg/dL
Triglycerides, Fasting		≥ 150 mg/dL

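### Laboratory relevance flags ignore the baseline value for 25 of 29 analytes, which dilutes the between-arm contrast; prolactin and total cholesterol are the main gap

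*SAP*

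**What the plan says.** SAP 9.2 defines the laboratory display as follows: "Potentially clinically relevant laboratory measurement test results in the double-blind treatment period will be identified for the Safety Sample". The results are summarized by treatment group and listed, using the criteria in SAP Appendix 2 (the same cuts as Protocol Appendix 3). Protocol 7.6.2 calls the output an incidence. Neither section limits it to subjects who were below the cut at baseline.

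Within Appendix 2, only two kinds of row look at baseline. Hematocrit adds "and decrease of ≥ 3 percentage points from Baseline", and urine protein, glucose and casts each need "Increase of ≥ 2 units".

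The vital-sign table (SAP Appendix 1) works differently. Its footnote requires that a value meet the criterion and "also represent a change from the subject’s baseline value of at least the magnitude shown" in the change column. The ECG table (SAP Appendix 3) has the same footnote. The laboratory table has none.

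Two other laboratory analyses are relevant. SAP 9.2 also plans "Summary statistics for mean and mean change from baseline in the routine clinical laboratory measurements", and it names prolactin among the measures. SAP 9.2.2 adds incidence by baseline category for fasting LDL, HDL, triglycerides and glucose.

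**The concern.** An incidence table for on-treatment laboratory abnormality is read as showing what happened on treatment. Under Appendix 2, a subject with fasting glucose of 115 mg/dL before and after dosing is counted, and so is one whose prolactin was above ULN before the first dose and stays there. Such subjects add a common background to both arms. The absolute difference shrinks, the ratio moves toward 1, and the extra counts add variance. A reader could then underrate a real laboratory effect, or take a high rate in both arms as something that arose on treatment.

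**Working it through.** **Count of criteria (SAP Appendix 2).** Sex-specific and fasting/nonfasting cuts are counted once per analyte. Chemistry 10, hematology 7, urinalysis 3, additional 9: 10 + 7 + 3 + 9 = 29. Four use baseline (hematocrit and the three urinalysis rows). 29 − 4 = 25, and 25/29 = 86%.

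**Where entry criteria already limit the problem.** Exclusion 21 (Protocol Table 3.4.3-1) removes subjects at or near the flag for creatinine, low platelets, low absolute neutrophil count and CPK (unless the medical monitor approves). It removes AST and ALT at a stricter level (above 2 × ULN, against a flag at 3 × ULN or more). That largely protects 6 of the 25 and leaves 25 − 6 = 19.

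**What SAP 9.2.2 covers.**
- LDL: below 160 to 160 or more, the same cut as Appendix 2. Covered.
- Triglycerides: below 150 to 150 or more, the same cut. Covered.
- HDL: 40 or more to below 40, for both sexes. This matches Appendix 2 for men only. A woman who falls from 52 to 45 mg/dL is flagged in Appendix 2 (below 50) but meets neither HDL row in 9.2.2, because 45 is not below 40 and the fall of 7 is less than 20.
- Glucose: every threshold row ends at 126 or more. There is a row for an increase of at least 10, but none for below 100 to 100 or more.
- Prolactin and total cholesterol: no row.

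The metabolic syndrome table in 9.2.2 is titled treatment-emergent but shows no baseline condition. The footnotes in 9.2.2 take baseline from Week 1, whereas SAP 9 uses the last value before the first dose and Protocol Table 3.7-1 schedules these laboratory tests only at screening and Day 21/ET.

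**Size.** The plan states no expected incidence for these flags, so there is no figure to reproduce. Let π be baseline prevalence, s the share of those still abnormal on treatment (taken as equal in both arms), and q the new-onset rate among the rest.

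All-subject flag rate = π·s + (1 − π)·q

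Difference between arms = (1 − π)·(q_drug − q_placebo)

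Assumed, not from the documents: s = 0.85, q = 0.10 on placebo and 0.20 on drug. Arm size is 160 (SAP 4, randomized), with everyone assumed to have a post-baseline value.

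At π = 0.20:
- Placebo: 0.20 × 0.85 + 0.80 × 0.10 = 0.17 + 0.08 = 0.25
- Drug: 0.17 + 0.80 × 0.20 = 0.33
- Difference: 0.08, against 0.10 among subjects not flagged at baseline
- Pre-existing share of placebo flags: 0.17/0.25 = 68%
- Difference over its standard error, all subjects: 0.08/√[(0.25×0.75 + 0.33×0.67)/160] = 0.08/0.0505 = 1.58
- The same among the 160 × 0.80 = 128 per arm not flagged at baseline: 0.10/√[(0.10×0.90 + 0.20×0.80)/128] = 0.10/0.0442 = 2.26

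The same steps at other prevalences:

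| π | Placebo | Drug | Difference (points) | Placebo flags pre-existing | Diff/SE, all | Diff/SE, not flagged at baseline |
|---|---|---|---|---|---|---|
| 2% | 0.115 | 0.213 | 9.8 | 15% | 2.39 | 2.50 |
| 10% | 0.175 | 0.265 | 9.0 | 49% | 1.95 | 2.40 |
| 20% | 0.250 | 0.330 | 8.0 | 68% | 1.58 | 2.26 |
| 30% | 0.325 | 0.395 | 7.0 | 78% | 1.31 | 2.12 |
| 40% | 0.400 | 0.460 | 6.0 | 85% | 1.09 | 1.96 |

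At 2% the two approaches nearly coincide. The loss grows with prevalence.

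**The case against.** The strongest reply is that this is one descriptive display among several. No test is planned on it. Mean change from baseline is reported for routine laboratory measures and for prolactin by name. SAP 9.2.1 gives a liver-injury table with thresholds relative to ULN or baseline, and 9.2.2 conditions on baseline for the most visible metabolic measures. Randomization balances the background in expectation. Restricting to subjects normal at baseline would hide worsening in those already abnormal. The list of planned tables in SAP Section 13 is redacted, so shift tables may exist.

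Most of this stands and limits the point. It does not remove it. Mean change does not show how many subjects newly crossed a threshold, and 9.2.2 has no row for prolactin or total cholesterol. The worry about hidden worsening is met by keeping both counts.

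A reader might go further and infer that pre-existing abnormality swamps any drug effect, so that the table cannot show one. The documents do not support that. The mechanism only dilutes, its size rests on prevalences that are not given, and in the illustration 6 to 10 points of difference remain.

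A reader might also take the glucose limit in exclusion 17, "Screening glucose must be ≤ 125 mg/dL (fasting) or < 200 mg/dL (nonfasting" mg/dL, as a general entry ceiling. It is a condition for subjects with non-insulin-dependent diabetes, and criterion 17 sets no numeric limit for others. Values of 100 to 125 mg/dL can enter either way, so the example holds, but for a different reason.

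Nor do the documents say that prolactin stays raised after washout. They show only that recent antipsychotic use is expected (Protocol Table 4.1-1).

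**Conclusion.** The point holds in a limited form. For 25 of 29 analytes the laboratory flags disregard baseline, out of line with the vital-sign and ECG tables, whose rows generally require a change (orthostatic hypotension and QTc are exceptions). Following the SAP as written counts unchanged abnormality as on-treatment incidence in both arms.

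The consequence is a weaker contrast, not a directional error, and the primary analysis is untouched. It matters only for flags that are common at baseline and not conditioned elsewhere: prolactin and total cholesterol first, then fasting glucose at 100 mg/dL and HDL below 50 mg/dL in women. Under the stated assumptions, a true 10-point difference appears as 9 points at 10% prevalence and 6 points at 40%. These figures are illustrative, since prevalence, persistence and new-onset rates are all assumed. Absence of a shift table is judged on the unredacted text only. This is a cheap improvement, not a defect that threatens the trial's conclusions.

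**What to change.** In SAP 9.2, add a treatment-emergent incidence for each Appendix 2 criterion. The numerator is subjects who meet the criterion on treatment but did not at baseline. The denominator is subjects with a baseline and a post-baseline value who did not meet it at baseline. Keep the all-subject flags as a second column or in the listing, so that worsening in subjects already abnormal stays visible. Leave the Appendix 2 cut-offs as they are, so the SAP stays in line with Protocol Appendix 3. In the same revision, reconcile the Week 1 baseline footnotes in 9.2.2 with the definition in SAP 9.

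The cost is SAP wording and one more column. Denominators will be smaller and will differ by test. Protocol Table 3.7-1 allows nonfasting blood at screening, so subjects with only a nonfasting screening sample drop out of the treatment-emergent column for fasting criteria. Screening blood may also be drawn before washout is complete, so baseline prolactin should be read with that in mind.

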9.2.1 Drug Induced Liver Injury (DILI)

Total bilirubin level should be checked for any subject with increased ALT or AST levels \geq three times the upper normal limits (ULN) or baseline.

- Reporting all DILI as SAE to the FDA based on Hy's Law:
 - AST or ALT $\geq 3 \times$ ULN or baseline and
 - T_Bili $\geq 2 \times$ ULN or baseline

A separate incidence table will be provided for DILI cases, and the corresponding listing will be provided for Safety Sample during the double-blind treatment period.

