5.3 Immediately Reportable Events

The investigator must immediately report after either the investigator or site personnel become aware of any SAE, potential serious hepatotoxicity, or confirmed pregnancy, by telephone, fax, or e-mail to the sponsor using the contact information on the cover page of this protocol. An IRE form must be completed and sent by e-mail, fax, or overnight courier to the sponsor. (Please note that the IRE form is NOT the AE ePlatform.)

Subjects experiencing SAEs should be followed clinically until their health has returned to baseline status, or until all parameters have returned to normal or have otherwise been explained. It is expected that the investigator will provide or arrange appropriate supportive care for the subject and will provide prompt updates on the subject's status to the sponsor.

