5.4 Potential Serious Hepatotoxicity

For a subject who experiences an elevation in AST or ALT that is ≥ 3 times ULN, a total bilirubin level should also be evaluated. If the total bilirubin is ≥ 2 times the ULN, complete an IRE form with all values listed and also report as an AE on the eSource.

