7.6.2 Clinical Laboratory Data

Summary statistics for changes from baseline in the routine clinical laboratory measurements and prolactin concentrations will be provided. In addition, the incidence of potentially clinically relevant values identified using prospectively defined in the SAP criteria for laboratory tests will be summarized.

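### SAP 9.2.1 lets a multiple of baseline stand in for a multiple of ULN in both limbs of its DILI rule, so subjects with normal liver values can be counted as DILI cases

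*SAP*

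**What the plan says.** SAP 9.2.1 has three parts.

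- **Trigger.** Total bilirubin is to be checked in subjects with increased ALT or AST at or above "three times the upper normal limits (ULN) or baseline".
- **Case rule.** Under a Hy's Law label, a case needs AST or ALT at least 3 times ULN or baseline, and total bilirubin at least 2 times ULN or baseline. The instruction attached to the rule is "Reporting all DILI as SAE to the FDA".
- **Output.** "A separate incidence table will be provided for DILI cases, and the corresponding listing will be provided for Safety Sample", for the double-blind period.

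SAP 9 defines a safety baseline as the last pre-dose observation, whether normal or abnormal.

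Protocol 5.4 has no baseline alternative. An AST or ALT of at least 3 times ULN prompts a bilirubin evaluation, and "If the total bilirubin is ≥ 2 times the ULN, complete an IRE form with all values listed". Protocol 5.3 makes this immediately reportable once site staff "become aware of any SAE, potential serious hepatotoxicity, or confirmed pregnancy".

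Protocol 7.6.2 leaves the laboratory criteria to the SAP: potentially clinically relevant values "identified using prospectively defined in the SAP criteria for laboratory tests will be summarized". Under SAP 9.2 such results "will be identified for the Safety Sample and will be summarized by treatment group and listed", using the Appendix 2 cuts. Those take each analyte separately: AST and ALT at 3 times ULN, and total bilirubin at an absolute 2.0 mg/dL.

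**The concern.** A multiple of a low-normal baseline can itself be a normal value. Without a floor at ULN, the rule can label a subject as a DILI case when ALT/AST, bilirubin or both never leave the normal range.

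The likely reason for a baseline alternative is to allow for subjects who enter with raised enzymes; Protocol 3.4.3 excludes AST or ALT only above 2 times ULN. As worded, the clause does nothing for them. When baseline is above ULN, 3 times ULN is the lower cut and already applies. The clause changes the result only for subjects whose baseline is below ULN.

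At stake are the DILI incidence table, its listing and the SAE reporting that the SAP attaches to the same rule. The table may also fail to reconcile with the events that sites report under Protocol 5.3 and 5.4. The Appendix 2 summaries cannot correct it, because they give no joint count of the two analytes.

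**Working it through.** The plan gives no figure to reproduce, so the check is of the rule itself.

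**Inputs.** The two limbs come from SAP 9.2.1 and the comparison rule from Protocol 5.4. All values are in multiples of ULN, with b the subject's baseline; normal means at or below 1.

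**Effective cuts under a plain OR.**

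- ALT/AST cut = 3 × min(1, b). For b = 0.25, 0.5, 0.75, 1 and 2 this gives 0.75, 1.5, 2.25, 3 and 3.
- Bilirubin cut = 2 × min(1, b). For b = 0.4, 0.5, 0.75 and 1 this gives 0.8, 1.0, 1.5 and 2.

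**When a normal value qualifies.** ALT/AST: 3b ≤ 1, so b ≤ 1/3. Bilirubin: 2b ≤ 1, so b ≤ 1/2. A subject with both analytes normal throughout needs both conditions, with at least a tripling of ALT or AST and a doubling of bilirubin.

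**Relation to Protocol 5.4.** Because min(1, b) ≤ 1, neither SAP cut exceeds the protocol cut. Every subject who meets Protocol 5.4 therefore meets the SAP rule on this reading.

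**Constructed subjects (baseline → on treatment).**

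| Subject | ALT | Bilirubin | SAP cuts (ALT; bilirubin) | SAP 9.2.1 | Protocol 5.4 |
|---|---|---|---|---|---|
| Both normal | 0.25 → 0.75 | 0.40 → 0.80 | 0.75; 0.80 | yes | no |
| Bilirubin normal | 1.0 → 3.0 | 0.45 → 0.90 | 3.0; 0.90 | yes | no |
| ALT normal | 0.30 → 0.95 | 0.9 → 2.0 | 0.90; 1.8 | yes | no |
| Both raised, below protocol cuts | 0.6 → 1.8 | 0.6 → 1.2 | 1.8; 1.2 | yes | no |
| ALT baseline just too high | 0.4 → 1.0 | 0.5 → 1.0 | 1.2; 1.0 | no | no |
| Bilirubin baseline just too high | 0.3 → 0.9 | 0.6 → 1.0 | 0.9; 1.2 | no | no |
| Clear case | 0.5 → 4.0 | 0.5 → 2.5 | 1.5; 1.0 | yes | yes |
| Raised ALT baseline | 1.5 → 3.2 | 0.5 → 2.2 | 3.0; 1.0 | yes | yes |

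**Frequency.** The documents give neither laboratory ULNs nor baseline liver distributions, so no rate can be computed. Both limbs must be met, and Protocol Table 3.7-1 schedules only one post-baseline chemistry draw (Day 21/ET). That points to a very low rate.

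**Effect of one extra case.** Assume one such subject in an arm of 160 (SAP 4) with no case under the protocol rule. Incidence moves from 0/160 (0%, Clopper-Pearson 95% CI 0 to 2.3%) to 1/160 (0.6%, 0.02 to 3.4%). This shows sensitivity to a single subject and does not predict how often it happens.

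**The case against.** **The trigger sentence speaks of increased levels, which suggests above normal.** The word is not tied to ULN and is absent from the two limbs that define a case. Nor does the trigger decide who can be classified: total bilirubin is in the routine chemistry panel (Protocol Table 3.7.3.2-1).

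**The authors may have meant baseline to replace ULN when baseline is already raised.** This is plausible, but the text does not say so. It would make the ALT/AST cut 3 × max(1, b). No all-normal subject would then count, but the last subject in the table would face a cut of 3 × 1.5 = 4.5 and drop out, although Protocol 5.4 captures that subject. The statement that no protocol case is lost thus belongs to the plain reading only. The ambiguity is itself a reason to reword.

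**Over-inclusion is the safe direction, and a listing is provided.** This largely stands. Flagged subjects can be reviewed individually, and the SAP does not change site reporting under Protocol 5.3 and 5.4. The output is nevertheless an incidence table of DILI cases as well as a screening list. How it is titled or laid out cannot be judged, because the list of tables is not visible.

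**Stronger readings that the documents do not support.** A reader might infer that the extra subjects are demonstrably not Hy's Law cases. Only SAP 9.2.1 names Hy's Law, and Protocol 5.4 does not use the term, so that claim needs an outside definition. A reader might also infer that the SAP breaches the protocol. Protocol 7.6.2 leaves the criteria to the SAP, so what can be said is that the two rules differ.

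**Conclusion.** Wrong as written; minor. Read plainly, SAP 9.2.1 lowers the DILI cut only for subjects whose baseline is below ULN, and it can count subjects whose ALT/AST, bilirubin or both stay normal. It also departs from the ULN-only rule in Protocol 5.4.

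The effect is confined to the DILI table and listing and the SAE reporting that the SAP ties to them. Efficacy analyses are untouched. A reader might infer a materially inflated hepatotoxicity signal; nothing in the documents shows that any such subject will occur. The conclusion rests on reading *or* as a plain alternative, which is how the words stand.

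**What to change.** In SAP 9.2.1, delete *or baseline* in all three places, so that the DILI table and listing use AST or ALT at least 3 times ULN and total bilirubin at least 2 times ULN, as in Protocol 5.4.

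If a more sensitive screen is wanted, put the baseline multiple in a separate labelled row that also requires the on-treatment value of each analyte to exceed ULN. Among the constructed subjects, that row would keep the one with both analytes raised (ALT 1.8, bilirubin 1.2) and leave out the three with a normal analyte. It would also match SAP practice elsewhere: Appendices 1 and 3 generally pair a change from baseline with a criterion value, and 9.2.2 gives change-only criteria their own rows.

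The cost is SAP wording and the matching table program. No new data or visits are needed.
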